Aim and objectives of the study:	
Study aim:
 
The aim of this clinical trial was to evaluate safety, tolerability, and efficacy, as well as to determine the optimal dose of XC221 co-administered with the standard symptomatic therapy to treat influenza and acute viral URI.
 
Study objectives:
 
1. To evaluate the safety of XC221 100 mg and 200 mg vs placebo, co-administered with the standard symptomatic therapy to treat influenza and acute viral URI by frequency of adverse events (AEs).2. To evaluate the efficacy of XC221 100 mg and 200 mg vs placebo, co-administered with the standard symptomatic therapy to treat influenza and acute viral URI by its effect on main manifestations of the disease (symptom intensity and duration) using the modified Jackson scale.3. To determine the optimal dose of XC221 among the suggested doses (100 and 200 mg per day) by analyzing efficacy, safety, and tolerability of IMP.4. To evaluate the dynamics of MxA protein blood concentration during the administration of XC221 100 mg and 200 mg vs placebo.5. To evaluate the dynamics of C-reactive protein (CRP) blood concentration during the administration of XC221 100 mg and 200 mg vs placebo.6. To evaluate the dynamics of blood concentrations of 6Ckine, BCA-1, CTACK, ENA-78, Eotaxin, Eotaxin-2, Eotaxin-3, Fractalkine, GCP-2, GM-CSF, Gro-α, Gro-β, I-309, IFN-γ, IL-1β, IL-2, IL-4, IL-6, IL-8, IL-10, IL-16, IP-10, I-TAC, MCP-1, MCP-2,

	
MCP-3, MCP-4, MDC, MIF, MIG, MIP-1α, MIP-1δ, MIP-3α, MIP-3β, MPIF-1, SCYB16, SDF-1$\alpha+\beta$, TARC, TECK, and TNF-α cytokines during the administration of XC221 100 mg and 200 mg vs placebo.

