	
At Visit 1 (before the first dose of IMP/placebo was taken), Visit 4, and Visit 6, patients' blood samples were collected to analyze serum concentrations of MxA protein, C-reactive protein, and cytokines 6Ckine, BCA-1, CTACK, ENA-78, Eotaxin, Eotaxin-2, Eotaxin-3, Fractalkine, GCP-2, GM-CSF, Gro-α, Gro-β, I-309, IFN-γ, IL-1β, IL-2, IL-4, IL-6, IL-8, IL-10, IL-16, IP-10, I-TAC, MCP-1, MCP-2, MCP-3, MCP-4, MDC, MIF, MIG, MIP-1α, MIP-1δ, MIP-3α, MIP-3β, MPIF-1, SCYB16, SDF-1α+β, TARC, TECK, and TNF-α.

The number of patients screened/randomized, and patients who completed the study	
Screened patients: 121 Randomized patients: 120 Patients who completed the study: 120

Inclusion criteria:	
1. Men and women aged 18 to 45 years (inclusive).2. Clinically diagnosed mild or moderate influenza or acute viral URI.3. Patient's body temperature at screening $\geq 37.5^{\circ}\text{C}$ and at least one intoxication or catarrhal symptom from the ones listed in the modified Jackson scale, with severity grade estimated as score ≥ 2.4. Uncomplicated course of influenza or acute viral URI based on assessment of clinical symptoms.5. The interval between the onset of the earliest symptoms of the disease and enrollment (administration of the first dose of IMP/placebo) is no longer than 36 hrs.6. Women of reproductive age (who are not in menopause and who have not undergone surgical sterilization) and men who have sexual activity should use a reliable method of contraception (acceptable methods of contraception in this study are: intrauterine devices, oral contraceptives, contraceptive patch, long-acting injectable contraceptives, a double barrier method (condom with spermicide, diaphragm with spermicide)) throughout the study period and 30 days after the last dose administration of IMP/placebo.7. A patient agrees to adhere to the treatment regimen, visits and laboratory examinations provided by the protocol.

	8. Signed Informed Consent Form.

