Exploratory endpoints	
1. Mean blood concentration of MxA protein in patient groups treated with XC221 100 mg and 200 mg XC221 as compared to the placebo group at Visit 4 and Visit 6;2. Changes in blood concentrations of MxA protein in patients at Visit 4 and Visit 6 as compared to Visit 1 in treatment groups;3. Mean blood concentration of C-reactive protein in patient groups treated with XC221 100 mg and 200 mg as compared to the placebo group at Visit 4 and Visit 6;4. Changes in blood concentrations of C-reactive protein in patients at Visit 4 and Visit 6 as compared to Visit 1 in treatment groups;5. Mean serum concentrations of 6Ckine, BCA-1, CTACK, ENA-78, Eotaxin, Eotaxin-2, Eotaxin-3, Fractalkine, GCP-2, GM-CSF, Gro-α, Gro-β, I-309, IFN-γ, IL-1β, IL-2, IL-4, IL-6, IL-8, IL-10, IL-16, IP-10, I-TAC, MCP-1, MCP-2, MCP-3, MCP-4, MDC, MIF, MIG, MIP-1α, MIP-1δ, MIP-3α, MIP-3β, MPIF-1, SCYB16, SDF-1α+β, TARC, TECK, TNF-α in patient groups treated with XC221 100 mg and 200 mg as compared to the placebo group at Visit 4 and Visit 6;6. Changes in serum concentrations of 6Ckine, BCA-1, CTACK, ENA-78, Eotaxin, Eotaxin-2, Eotaxin-3, Fractalkine, GCP-2, GM-CSF, Gro-α, Gro-β, I-309, IFN-γ, IL-1β, IL-2, IL-4, IL-6, IL-8, IL-10, IL-16, IP-10, I-TAC, MCP-1, MCP-2, MCP-3, MCP-4, MDC, MIF, MIG, MIP-1α, MIP-1δ, MIP-3α, MIP-3β, MPIF-1, SCYB16, SDF-1α+β, TARC, TECK, TNF-α in patients at Visit 4 and Visit 6 as compared to Visit 1 in treatment groups;7. Evaluation of the relationship between cytokine concentration and the modified Jackson scale score.
Statistical methods	
Hypothesis testing
 
In accordance with the aim and objectives of the trial, a hypothesis that time to sustained improvement of clinical symptoms based on the modified Jackson scale differs between the groups was formulated for the primary endpoint.

The groups were compared for the parameter "time to sustained improvement of clinical symptoms" using the generalized Wilcoxon test (the Gehan–Wilcoxon test). The null hypothesis stated that there were no differences between two groups for the hazard function assessed for the primary endpoint in each IMP group as compared to the placebo group. It was assumed that if the Z-score is higher than the selected α -quantile of the standard normal distribution, the null hypothesis will be rejected in favor of the alternative hypothesis stating that there is difference between the two groups.

Sample size justification

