All variables for analysis were presented using the descriptive statistical methods. An analysis was conducted to compare groups at primary and secondary endpoints. Categorical variables were analyzed using the χ^2 test; the two-tailed Fisher's exact test was used if more than 20% of expected frequencies were < 5. The areas under "variable versus time" curves were calculated using the trapezoidal rule. Groups were compared in terms of quantitative variables using ANOVA/ANCOVA; the non-parametric alternative was employed if the assumptions underlying the method were not met. Survival analysis (plotting the Kaplan–Meier curves, comparing the hazard functions using the Gehan–Wilcoxon test) and the stratified Cox regression model were used for the censored Time-to-Event data. The secondary endpoint data for patients prematurely withdrawn from the study were substituted using the LOCF algorithm.

Interim analysis

Interim analysis was not involved in this study.

Analysis groups

Three equal-sized groups, with 40 subjects per group (2 groups receiving different doses of IMP and the placebo group) were planned for this study. The groups treated with IMP were supposed to be compared in a pairwise manner to the placebo group; it was also planned that the treatment groups would be compared to each other.

Baseline comparability

The baseline data (demographic and anthropometric characteristics, as well as disease duration documented prior to treatment initiation) were compared between the groups in the Full Analysis Set population. If significant differences between treatment groups were revealed for any baseline parameter, sensitivity analysis was performed to test

whether the conclusions about the efficacy remained unchanged after applying a correction for different baseline parameters in groups.

Safety analysis

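### Biomarker endpoints do not state a placebo comparison that uses the Visit 1 value; ANCOVA on log concentration would give a more precise one from the samples already drawn

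*Combined protocol and SAP*

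**What the plan says.** All references are to the combined protocol and SAP.

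- **Aim and objectives of the study.** Objective 4 reads "To evaluate the dynamics of MxA protein blood concentration during the administration of XC221 100 mg and 200 mg vs placebo". Objectives 5 and 6 take the same form for CRP and for 40 cytokines, so 42 markers are involved.
- **Methodology (study design and procedures).** Blood is drawn "At Visit 1 (before the first dose of IMP/placebo was taken), Visit 4, and Visit 6". A pre-dose value is therefore planned for every patient.
- **Exploratory endpoints 1, 3 and 5.** These are levels at a visit against placebo. Endpoint 1 begins "Mean blood concentration of MxA protein in patient groups treated with XC221 100 mg and 200 mg XC221 as compared to the placebo group", and all three are taken "as compared to the placebo group at Visit 4 and Visit 6". Visit 1 does not appear.
- **Exploratory endpoints 2, 4 and 6.** These are changes from baseline. Endpoint 2 is "Changes in blood concentrations of MxA protein in patients at Visit 4 and Visit 6 as compared to Visit 1 in treatment groups". No comparator is named.
- **Statistical methods, Statistical methodology.** "Groups were compared in terms of quantitative variables using ANOVA/ANCOVA", and "the non-parametric alternative was employed if the assumptions underlying the method were not met". No covariate is given, nor a rule for choosing ANOVA or ANCOVA, nor a transformation. The sentence on scope is "An analysis was conducted to compare groups at primary and secondary endpoints"; exploratory endpoints are not mentioned there.
- **Statistical methods, Analysis groups.** Each dose is to be compared with placebo, and the doses with each other.
- **Statistical methods, Baseline comparability.** The variables checked are demographic, anthropometric and disease duration. Biomarkers are not among them.
- **Statistical methods, Efficacy analysis.** The analysis population for CRP and the cytokines is given, but no model.

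**The concern.** The objectives concern change over time relative to placebo. One set of endpoints has the placebo contrast without the baseline. The other has the baseline without a stated placebo contrast. No endpoint joins the two, and the general methods text does not do so for them.

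Two things are at stake. The first is precision: if a marker at Visit 4 or 6 is correlated with its value at Visit 1, a comparison that ignores Visit 1 leaves explainable variance in the error term. The second is interpretation. In an acute self-limiting infection, markers can be expected to move towards normal in every arm, so a change from Visit 1 says little about the drug until it is set against the change on placebo. The plan should say that this comparison is made, and how.

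**Working it through.** **Inputs from the documents.** There are 40 patients per arm (Sample size justification; Analysis groups). The plan states no sample size for the biomarkers. The 40 comes from the primary endpoint and reproduces: with a hazard rate of 1.23, 37 events give an exact 95% CI width of 0.791, within the target of 0.8 (36 events give 0.802); 37/0.95 = 38.9, so 39; and 39/0.975 = 40.

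**Inputs assumed.** The documents give no marker SD and no correlation rho between the Visit 1 and follow-up values. I take log SD = 1, a true dose-to-placebo ratio of 0.6, two-sided alpha of 0.05, and rho of 0.2 to 0.7.

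**Step 1, relative variance of the between-arm contrast on the log scale.** The unadjusted visit mean has variance 1, between-arm change from Visit 1 has 2(1 - rho), and ANCOVA on Visit 1 has 1 - rho².

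| rho | visit mean | change | ANCOVA | equivalent n per arm, 40/(1 - rho²) |
|---|---|---|---|---|
| 0.2 | 1 | 1.6 | 0.96 | 42 |
| 0.3 | 1 | 1.4 | 0.91 | 44 |
| 0.5 | 1 | 1.0 | 0.75 | 53 |
| 0.7 | 1 | 0.6 | 0.51 | 78 |

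ANCOVA has the smallest variance in every row. Comparing change between arms beats the plain visit mean only when rho exceeds 0.5.

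**Step 2, power on the log scale.** The effect is |ln 0.6| = 0.511. The unadjusted standard error is √(2/40) = 0.2236, so the standardised effect is 0.511/0.2236 = 2.284. Power is approximately Φ(2.284/√(1 - rho²) - 1.96).

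- Unadjusted: Φ(0.324) = 63%
- rho 0.2: Φ(2.332 - 1.96) = 64%
- rho 0.3: Φ(2.395 - 1.96) = 67%
- rho 0.5: Φ(2.638 - 1.96) = 75%
- rho 0.7: Φ(3.199 - 1.96) = 89%

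Simulation, which uses t critical values and estimates the slope, gives slightly lower figures: about 61% unadjusted, and about 64%, 72% and 89% with ANCOVA at rho 0.3, 0.5 and 0.7. At rho 0.2 the gain is about one point.

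**Step 3, separating the log transform from the baseline adjustment.** In simulated log-normal data with the same settings, power at rho 0.3, 0.5 and 0.7 is:

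| Analysis | 0.3 | 0.5 | 0.7 |
|---|---|---|---|
| t-test on raw visit values | 44% | 44% | 44% |
| rank test on visit values | 59% | 58% | 60% |
| t-test on log visit values | 63% | 61% | 61% |
| rank ANCOVA with Visit 1 | 63% | 69% | 85% |
| log ANCOVA with Visit 1 | 65% | 73% | 88% |

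These runs differ from the Step 2 simulation figures only by simulation error. At rho 0.3 almost all of the gain over raw values comes from taking logs, and Visit 1 adds about 2 points. At rho 0.7 Visit 1 adds about 27. If skewness triggers the plan's non-parametric route, the rank-test row is the fairer starting point.

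**Step 4, chance imbalance at Visit 1.** The probability that two arms differ by more than 0.3 SD is 2(1 - Φ(0.3/0.2236)) = 2(1 - Φ(1.342)) = 18% per marker. The unadjusted test already allows for this as sampling error. ANCOVA removes the part that carries forward.

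**The case against.** **What stands.** The endpoint list need not be read as excluding a placebo comparison of change. The phrase *in treatment groups* is used inconsistently: Sample size justification sets the placebo group apart from the treatment groups, while Baseline comparability uses the term for all arms. Objectives 4 to 6 are framed against placebo, and Analysis groups plans pairwise comparisons with placebo. ANCOVA is listed, and short endpoint labels seldom name covariates, so adjustment is unspecified rather than ruled out. The non-parametric alternative is not described, so it could keep the Visit 1 value. Randomisation makes the visit-mean contrasts valid as they are.

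**Stronger readings that the documents do not support.**

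- *Change will be tested within arms and read as drug effect.* No section says so, and each change endpoint is paired with a placebo-controlled endpoint for the same marker. The hazard is conditional. If change were tested within one arm of 40, with an assumed 40% natural fall and no drug effect, a paired log-scale test would be significant in 76%, 88% and 98% of trials at rho 0.3, 0.5 and 0.7.
- *The Visit 1 sample is wasted.* It is the reference for endpoints 2, 4 and 6.
- *The plan uses the least precise contrast.* Between-arm change is less precise than the visit mean whenever rho is below 0.5.

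**What the objection leaves.** No section names Visit 1 as a biomarker covariate, plans a log transform, or says how change is to be compared with placebo. A reader cannot recover the intended model from the text.

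**Conclusion.** The point holds as one of precision and specification, not bias. As defined, the between-arm contrasts for MxA, CRP and the cytokines omit the Visit 1 value, and the role of placebo in the change endpoints is left open. A baseline-adjusted log-scale contrast answers objectives 4 to 6 directly and is at least as precise at any correlation, apart from the trivial cost of estimating one slope.

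The size depends on a correlation that the documents do not give. The cut in variance is 4% at rho 0.2, 9% at 0.3, 25% at 0.5 and 49% at 0.7. The power figures further assume log-normal markers with log SD 1 and a ratio of 0.6. If follow-up values are only weakly related to Visit 1, most of the improvement comes from the log transform alone.

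Importance is low. The endpoints are exploratory, and the dose-selection rule in Sample size justification rests on median time to the primary endpoint and on safety. Nothing here touches the primary analysis.

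**What to change.** For each marker, state a single model: log concentration at Visits 4 and 6, analysed by ANCOVA at each visit or by a repeated-measures model, with treatment group as factor and log Visit 1 concentration as covariate. Report the geometric mean ratio with 95% CI for 100 mg versus placebo, 200 mg versus placebo and 200 mg versus 100 mg. Say explicitly that this covers the exploratory endpoints. Keep within-arm change from Visit 1 as a descriptive summary and label it so. If the log-scale model does not fit, use a rank method that keeps the Visit 1 value, such as rank ANCOVA.

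The cost is a few lines of analysis text and a different model call, with no extra patients, samples or assays. The synopsis reports 120 patients as having completed, so if the biomarker results have already been examined, the adjusted analysis should be added and labelled as specified afterwards.

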
It was expected that the optimal dose of the investigational medicinal product (XC221 100 mg or XC221 200 mg) would be selected in this trial by exploratory data analysis. The optimal IMP dose was supposed to be selected by the Sponsor according to the treatment group that would have the minimum median time to reach the effect for the primary endpoint but a similar or superior safety profile compared to that in the remaining groups. It was assumed that if the median time to reach the effect for the primary endpoint in two dose groups was equal, the smaller dose would be selected.

The sample size was calculated using the PASS 14 software according to the data obtained in the previous trial of the same Sponsor (FLU-XC8-01). In it, the hazard rates for a similar endpoint were found to be 0.83 and 1.23 for the placebo and treatment groups, respectively. The sample size for the present trial was estimated so that the width of 95% two-sided confidence interval of hazard rate was no greater than the twofold difference in hazard rates between the treatment and placebo groups in a similar study (0.8); the percentage of censored observations was $\leq 5\%$. Hence, it was found that the sample size required per group was 39 subjects. The selected significance level $\alpha = 0.05$; the pre-set power was 80%. Having assumed that the percentage of patients withdrawn throughout the study was 2.5%, 40 patients needed to be screened for each group. Size of the placebo group was equal to that of the treatment groups. Hence, a total of 120 patients were planned to be randomly assigned into three groups at a 1:1:1 allocation ratio (40 subjects into each group: the placebo group and the groups treated with XC221 100 mg or XC221 200 mg). Assuming

that the probability of subject withdrawal at screening was ~15%, up to 140 patients were to be screened.

This was a multicenter trial, with patients recruited on a competitive basis. In order to minimize the bias, each study center could randomize no more than 30% (36 patients) of the total sample size.

Statistical methodology

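### The primary rejection rule is worded as an upper-tail test although its alternative is non-directional, and neither the critical value nor the sign of Z is stated

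*Combined protocol and SAP*

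**What the plan says.** Under Statistical methods, Hypothesis testing, the combined protocol and SAP states the primary hypothesis as "time to sustained improvement of clinical symptoms based on the modified Jackson scale differs between the groups". The null is no difference in the hazard function "in each IMP group as compared to the placebo group", and the null is to be given up in favour of the "alternative hypothesis stating that there is difference between the two groups". Hypothesis and alternative are both non-directional. The test is the Gehan-Wilcoxon test.

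The rejection rule in the same section is that "if the Z-score is higher than the selected α -quantile of the standard normal distribution, the null hypothesis will be rejected".

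Other places that bear on sidedness:
- Sample size justification sets α at 0.05 without saying one- or two-sided. The trial is sized on the width of a "95% two-sided confidence interval of hazard rate".
- Statistical methodology calls Fisher's exact test two-tailed. It names the Gehan-Wilcoxon test again without sidedness.
- The section on patient numbers reports "Patients who completed the study: 120", so the trial is over.

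**The concern.** An alternative that covers a difference in either direction needs a rejection region in both tails. The written region lies in one tail, above a single quantile, and three things needed to apply it are missing: which quantile was selected, whether Z or |Z| is compared with it, and which group's advantage makes Z positive.

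Two consequences follow. First, a one-tailed region cannot detect a difference in the other direction, although the hypothesis covers it. Second, someone applying the sentence could use different cut-offs, with different error rates, and each choice could be defended from the text. This is the only rejection rule given for the primary endpoint, so nothing else in the plan settles the question.

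**Working it through.** **Inputs.** From Sample size justification: hazard rates 0.83 (placebo) and 1.23 (treatment), censoring of at most 5%, interval width of at most 0.8, 39 per group (40 after 2.5% withdrawal), α = 0.05. Assumed here: exponential times.

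**1. The plan's own figure.** The width limit is twice the hazard difference: 2 × (1.23 − 0.83) = 0.8. For an exponential hazard λ with E events, the 95% two-sided interval has width λ(χ²[0.975; 2E] − χ²[0.025; 2E])/(2E). With λ = 1.23:
- E = 36: width 0.802, too wide.
- E = 37: width 0.791, acceptable.

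Then 37/0.95 = 38.9, which rounds up to 39, and 39/0.975 = 40. Both stated figures reproduce. With a 90% interval, 27 per group (27 × 0.95 = 25.65 expected events, width 0.795) would have been enough. The sizing therefore follows the two-sided 95% convention and does not use the rejection rule.

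**2. What the sentence could mean at α = 0.05.**

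| Reading | Total size | Rejects in |
|---|---|---|
| Z > 1.645 | 0.05 | upper tail only |
| Z > 1.960 | 0.025 | upper tail only |
| \|Z\| > 1.645 | 0.10 | both tails |
| \|Z\| > 1.960 | 0.05 | both tails |

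Taken strictly, the 0.05 quantile is −1.645. Rejecting above it has size 0.95 and is plainly not meant.

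**3. Consequences, by simulation.** Gehan-Wilcoxon Z (weights equal to the number at risk), 40 per arm, 5% censored at a uniform fraction of the event time, 40,000 runs. Positive Z is taken as faster improvement on the dose, which is a convention chosen here because the plan gives none.

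| True situation | Z > 1.645 | \|Z\| > 1.96 |
|---|---|---|
| No difference | 4.9% (all upper tail) | 4.8% (2.4% in the upper tail) |
| Dose 1.23, placebo 0.83 | 43.2% | 31.1% |
| Dose 0.83, placebo 1.23 | 0.1% | 31.4% |

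Separately programmed repeats gave 5.2% to 5.3% and 2.6% for the upper tail with no difference, so about 5% and 2.5% are fair summaries.

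**4. Hand check.** At the plan's hazards Z has mean 1.47 and SD 1.00.
- P(Z > 1.645) = 1 − Φ(1.645 − 1.47) = 1 − Φ(0.175) = 0.43.
- P(Z > 1.96) = 1 − Φ(0.49) = 0.31. The lower tail adds only Φ(−3.43) = 0.0003, so Z > 1.96 and |Z| > 1.96 perform alike when the effect is positive.
- With the hazards reversed the mean is −1.47: P(Z > 1.645) = 1 − Φ(3.115) = 0.0009 and P(Z > 1.96) = 1 − Φ(3.43) = 0.0003.

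Both upper-tail readings thus lose the negative direction. Only the 1.645 reading changes the positive direction, by 43.2 − 31.1 = about 12 percentage points.

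**5. Sign reversed.** If positive Z meant slower improvement on the dose, the rows for faster and slower dose would swap. Z > 1.645 would then find a truly faster dose in about 0.1% of trials.

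**6. Sensitivity of the 12 points.** They are about 12 with 39 per arm and also with twice-daily assessment (hazards assumed per day, since the plan gives no unit). They are about 8 at an assumed hazard ratio of 1.25 and about 9 at 2.0.

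**The case against.** The strongest reply is that a two-sided 5% test was plainly meant. Hypothesis, null and alternative are all non-directional, the sizing interval is two-sided at 95%, the one test whose sidedness is given is two-tailed, and no superiority or one-sided hypothesis appears anywhere. On that view the fault is a missing absolute value and a missing division by two. This largely stands: two-sided is the likely intent. It does not make the written rule correct, because the rule still omits half of the region that the alternative requires.

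A reader might go further and infer that the plan doubles the false-benefit rate, or that any Z between 1.645 and 1.96 was called significant. The documents do not support that. They do not give 1.645 or say which quantile was selected, and they do not say that positive Z means benefit. With Z > 1.96 the upper-tail error equals that of the two-sided test. The doubling needs both unstated choices together.

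It is also fair to say that this is not the only decision rule on the primary endpoint. Sample size justification selects the dose by shortest median time, subject to safety, in an exploratory analysis. That rule does not use Z, so the dose-finding aim does not depend on the faulty sentence. The primary comparison with placebo does, and Efficacy analysis calls it the main efficacy analysis.

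**Conclusion.** The defect is real and minor. The wording gap is certain: a non-directional alternative is paired with an upper-tail region that has no absolute value, α/2, critical value or sign convention.

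The size of the effect depends on the reading:
- **Any upper-tail reading:** a difference in the negative-Z direction is declared in about 0.1% of trials or fewer, against about 31% for a two-sided 5% test.
- **Cut-off 1.645 with positive Z meaning faster improvement on the dose:** false-benefit rate per dose about 5% instead of about 2.5%, and significance at hazards 1.23 against 0.83 about 43% instead of about 31%.
- **Cut-off 1.96 with the same sign:** neither figure changes.

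These results assume exponential times, 5% censoring, 40 per arm and the plan's hazards. They are not the probability that this trial's conclusion is wrong, and nothing in the documents shows that a one-sided test was run. The 31% and 43% fall below the 80% power mentioned in the plan; that is a separate matter, since 39 per group comes from an interval width.

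**What to change.** Replace the rejection sentence with: *H0 is rejected for a dose versus placebo if |Z| exceeds the (1 − α/2) quantile of the standard normal distribution (1.96 for α = 0.05), equivalently if the two-sided p-value is below 0.05.* The absolute value removes the need for a sign convention in the test, but the direction of effect must still be reported.

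A corrected sentence cannot prespecify anything after completion. The sponsor should therefore also confirm which rule was applied and report, for each dose versus placebo, the two-sided p-value and the direction of effect.

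Cost: one sentence and one confirmation, with no change to sample size or dose selection. If a two-sided test was used, nothing is lost. If Z > 1.645 with positive Z as benefit was used, the chance of significance at the plan's hazards falls from about 43% to about 31%, and a result between the two cut-offs would no longer count as significant. The change sets the cut-off for each comparison only and leaves multiplicity across the two doses open.

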The safety population consisted of all the patients treated with any dose of IMP/placebo. Safety parameters (vital signs, laboratory data, and AEs) were descriptively analyzed for each group. The numbers of AEs and patients with AEs were summarized according to their treatment group and categorized according to the system organ classes and preferred terms. Additional summarizing was performed for severity of AEs and their relationship to IMP. SAE narratives were additionally made in a separate analysis. Patients withdrawn prematurely from the trial can be found in the list of patients and were categorized according to the main reason for withdrawal (in each treatment group).

Tolerability analysis

Frequency tables were plotted to analyze the tolerability data (in the safety population); a conclusion regarding the potential differences in tolerability between the analyzed samples was drawn according to these tables.

Efficacy analysis

The main efficacy analysis for the primary endpoint was carried out using the Full Analysis Set population. Sensitivity analysis in the population of patients with verified viral infection and the Per Protocol population was conducted. Sensitivity analysis using the stratified Cox model was carried out separately for the Per Protocol population, with the following covariates: "study center", "presence of viral infection", and "concomitant treatment with NSAIDs".

Secondary endpoint analysis was conducted in the Full Analysis Set population and the population of patients with verified viral infection. Concentrations of C-reactive protein and 6Ckine, BCA-1, CTACK, ENA-78, Eotaxin, Eotaxin-2, Eotaxin-3, Fractalkine, GCP-2, GM-CSF, Gro- α , Gro- β , I-309, IFN- γ , IL-1 β , IL-2, IL-4, IL-6, IL-8, IL-10, IL-16, IP-10, I-TAC, MCP-1, MCP-2, MCP-3, MCP-4, MDC, MIF, MIG, MIP-1 α , MIP-1 δ , MIP-3 α , MIP-3 β , MPIF-1, SCYB16, SDF-1 $\alpha+\beta$, TARC, TECK, and TNF- α cytokines were analyzed in the Full Analysis Set population.

	
Software
 
Specialized SAS software (version 9.4) was used for statistical analysis.

--	---

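### The stated 80% power is not a property of this design: N comes from a confidence-interval width, and at the cited hazard rates each dose-versus-placebo test has about 30–33% power two-sided (41–45% one-sided)

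*Combined protocol and SAP*

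**What the plan says.** Under Statistical methods, Sample size justification, the combined protocol and SAP takes its inputs from an earlier trial of the same sponsor, where the "hazard rates for a similar endpoint were found to be 0.83 and 1.23 for the placebo and treatment groups", respectively. The size was then "estimated so that the width of 95% two-sided confidence interval of hazard rate was no greater than the twofold difference in hazard rates" between the arms, given as 0.8, with at most 5% of observations censored. This leads to 39 per group, raised to 40 for 2.5% withdrawal. The same paragraph adds a significance level of 0.05 and says that "the pre-set power was 80"%. It names no effect or test for that power.

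The section also says that the optimal dose "would be selected in this trial by exploratory data analysis", on the basis of the shortest median time and the safety profile.

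Under Hypothesis testing, the primary endpoint is compared by the Gehan–Wilcoxon test, each dose against placebo: "The null hypothesis stated that there were no differences between two groups for the hazard function". Rejection follows "if the Z-score is higher than the selected" α-quantile, which reads as one-sided. Yet "the null hypothesis will be rejected in favor of the alternative hypothesis stating that there is difference between the two groups", which reads as two-sided. Under Efficacy analysis, "The main efficacy analysis for the primary endpoint was carried out using the Full Analysis Set population".

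**The concern.** A confidence-interval width fixes how precisely one group's hazard rate is estimated. It says nothing about the probability that a test between two groups rejects. A power figure needs a test, an effect, a significance level and a number of events; here only the level and, indirectly, the events are given. Stated beside the sample size, the 80% will be read as the power of the planned primary comparison.

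What is at stake is how a non-significant result is read. With 80% power, a miss would be a 20% event and a null result would be fairly strong evidence against the effect. If the true power is nearer one third, a null result says little.

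**Working it through.** **Inputs.** From Sample size justification: rates 0.83 (placebo) and 1.23 (treatment), maximum width 0.8, censoring at most 5%, withdrawal 2.5%, α = 0.05. From Hypothesis testing: the Gehan–Wilcoxon test, each dose against placebo.

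**1. Reproducing the plan's N.** The limit is 2 × (1.23 − 0.83) = 0.80. For a constant hazard h estimated from E events, the exact interval has width

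h × [χ²(0.975; 2E) − χ²(0.025; 2E)] / (2E).

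- h = 1.23: E = 36 gives 0.802 (too wide); E = 37 gives 0.791 (met).
- 37 / 0.95 = 38.95, so 39. Then 39 / 0.975 = 40.
- h = 0.83: E = 17 already suffices (0.785), so the 1.23 rate drives N.

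The plan's 39 and 40 are reproduced, and power is not used.

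**2. Log-rank approximation at the cited rates.** HR = 1.23 / 0.83 = 1.482; ln HR = 0.3933. With 37 events per arm:

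- SE = √(2/37) = 0.2325, and the expected Z = 0.3933 / 0.2325 = 1.692.
- Two-sided power = Φ(1.692 − 1.96) = 39.4%.
- One-sided power = Φ(1.692 − 1.645) = 51.9%.
- Expected 95% interval for the HR = exp(0.3933 ± 1.96 × 0.2325) = 0.94 to 2.34.
- Events for 80% power: 4 × (1.96 + 0.8416)² / 0.3933² = 203 two-sided; with 1.645 in place of 1.96, 160 one-sided. About 74–80 are available per comparison.

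**3. The planned Gehan–Wilcoxon test.** Simulation with exponential times at 0.83 and 1.23, 20,000 runs per row, α = 0.05:

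| n per arm, censoring | Gehan 2-sided | Gehan 1-sided | Log-rank 2-sided | Log-rank 1-sided |
|---|---|---|---|---|
| 39, 5% random | 30.6% | 42.3% | 38.8% | 51.0% |
| 39, 5% administrative | 31.5% | 43.5% | 38.6% | 51.4% |
| 40, 5% random | 31.5% | 43.7% | 40.1% | 52.5% |
| 40, none | 33.2% | 45.3% | 41.3% | 53.9% |

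With no treatment effect the two-sided Gehan rejection rate is 5.0%. A separate simulation of 6,000 runs per setting gave 29.4–32.8% two-sided and 41.0–44.8% one-sided. If the rates are per day (the unit is not stated), rounding times to a 12-hour grid gave 29.8% and 41.8% at 40 per arm with 5% censoring.

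**4. What would give 80%.**

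- At HR 1.48, the two-sided Gehan test reaches 79.0% with 140 per arm and 80.5% with 145.
- At 39 per arm, it reaches 77.2% at HR 2.10 and 79.2% at HR 2.15. No such effect appears in the plan.
- Pooling both doses against placebo gives only 50–53% two-sided or 62–65% one-sided by the log-rank formula.

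**5. Sensitivity to the shape of the time distribution (40 per arm, Gehan two-sided).**

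- HR held at 1.48, Weibull shape 0.7, 1.5 and 2: 31.6%, 31.4% and 31.2%.
- 1.48 read instead as a ratio of times, shape 1, 1.5 and 2: 31.5%, 59.1% and 82.9%. At shape 2 the implied HR is 1.4819² = 2.20.

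**The case against.** The strongest reply is that the effect used here is not one the plan declares. The two rates serve only to set a width, they belong to a similar endpoint in another trial, and the plan gives neither a hazard ratio nor a proportional-hazards model. If each rate is events over person-time, 1.48 is a ratio of mean times and equals the hazard ratio only when times are exponential. A rising hazard is plausible, because patients enter with at least one symptom scored 2 or more and must then bring every symptom to 1 or below on three consecutive evaluations. On that reading, power is 59% at Weibull shape 1.5 and 83% at shape 2. It can also be said that precision-based sizing is legitimate for exploratory dose selection, and that with 120 patients randomized and completed, N can no longer change.

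Part of this stands. The 30–33% is conditional and must be labelled so; an effect concentrated early could also raise Gehan power. N is correct for its own criterion, and dose selection is unaffected. But none of it supports the stated 80%. The plan quotes hazard rates, and its N is reproduced by a constant-hazard interval, under which the two ratios coincide and power is about 31%. Reaching 80% needs both the time-ratio reading and a strongly rising hazard, neither of which is in the plan. The word exploratory is applied to dose selection, while a formal null hypothesis, a rejection rule and a main efficacy analysis remain.

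**Conclusion.** The power statement is wrong as written. The sample size rests on interval width alone, and the 80% is linked to no effect or test.

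At the only rates the plan cites, each dose-versus-placebo Gehan–Wilcoxon test has about 30–33% power two-sided or 41–45% one-sided. The corresponding chance of a miss is about 67–70% or 55–59%. These figures assume a hazard ratio of 1.48, proportional hazards, 39–40 patients per arm, 0–5% censoring and no multiplicity adjustment for two doses; any adjustment would lower them.

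The conclusion that 80% is underived needs none of these assumptions. Confidence is high.

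**What to change.** In Sample size justification:

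- Withdraw the 80% power clause. If the wording must stay as a record of planning, annotate it as not derived from the calculation.
- State that N was chosen for precision: interval width at most 0.8 at a hazard of 1.23, hence 37 events, 39 patients at 5% censoring and 40 with 2.5% withdrawal.
- Give power only as a conditional figure with its assumptions: about 30–33% two-sided (41–45% one-sided) for Gehan–Wilcoxon at a hazard ratio of 1.48 under proportional hazards. Note that reading 1.48 as a time ratio with a rising hazard gives higher values.

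In Hypothesis testing, state whether the test is one- or two-sided.

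Present the expected hazard-ratio interval (about 0.94 to 2.34 at 1.48) beside the test, so that a non-significant result is not read as absence of effect.

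The cost is wording and a less favourable power figure. No patients are added, and the primary test and dose-selection rule stay as they are.
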